### **Secondary Analysis**

Secondary analyses will compare CSA during usual care period and the individual interventions using identical methods:

- effects on AF and potentially lethal arrhythmias (asystole, sustained VT, bradycardia for  $\geq 6$  seconds) will be separately assessed as secondary endpoints
- Exploratory analyses will assess association of dialysis day (Monday/Wednesday/Friday or Tuesday/Thursday/Saturday), shift (1st-3rd), and site with CSA

Data for the optional substudy will be analyzed using machine learning algorithms to detect any associations between EKG morphology and baseline electrolyte concentration.

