**Dialysate Interventions Trial (Study A)**—This trial will test the impact of dialysate K and HCO3 on CSA. After a month of usual care, subjects will cross-over in random order to four month-long periods using alternative approaches to algorithm-specified manipulation of dialysate K or HCO3 guided by POC-obtained laboratory testing prior to each dialysis. There will be a one-week washout with usual care between each intervention period. Randomization sequences will be balanced with respect to treatments to minimize impact of sequence or carryover effects on outcomes. Algorithms tested will compare **a) Minimization of dialysate-serum potassium gradient vs. maximization of potassium removal** (preferential use of high potassium dialysate to minimize gradient vs. low K dialysate to maximize removal); and **b) Alkalosis avoidance vs. acidosis avoidance** (preferential use of lower dialysate HCO3 concentration vs. higher dialysate HCO3). Subjects and investigators will be blinded to the intervention in use. HD nurses and staff will obtain POC chemistry results prior to each HD session and adjust the prescription for dialysate potassium or HCO3 as dictated by the algorithm. Since dialysate prescription changes must be entered manually, dialysis staff cannot be blinded to the algorithms, but they will not assess endpoints or be otherwise involved in interpretation of study data.

Whole blood (100  $\mu$ L) will be obtained by dialysis staff when the catheter, fistula or graft is accessed prior to each HD session during the K and HCO3 intervention periods. Blood will be drawn into a non-heparinized syringe and added to the i-STAT cartridge for immediate testing—a process similar to routine blood glucose testing during HD. Blood will be immediately tested on the i-STAT according to the manufacturer's protocol. (Alternatively blood may be drawn into heparinized tubes, mixed by inversion, and tested within 10 minutes). Results are saved on the device, printed, and can be entered directly to the study data-base.

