After ILR placement, subjects will crossover between two UF rate interventions: 1) UF rate-restricted dialysis, in which UF rates are limited to a maximum of 10 mL/kg/hr for the duration of the session 2) UF rate-unrestricted dialysis. It is anticipated that patients with large interdialytic weight gains in the UF rate-restricted intervention may not achieve their target post-dialysis weight during the prescribed treatment time. In order to prevent progressive volume overload and the need for additional HD sessions to manage volume gains in this scenario, subjects will crossover weekly between the restricted

and unrestricted UF interventions. This weekly crossover accomplishes two important goals: First, it reduces safety concerns by ensure that any volume gained due to limiting the UF are constrained to one week and promptly addressed with unlimited UF the following week. Second, it increases separation between UF rates in the two interventions, since a higher UF-rate will be needed to address any weight and volume gains resulting from UF-rate restriction.

Investigators will be blinded. Subjects will not be blinded as it is not feasible to blind them to the goal UF and post-dialysis weight (typically self-measured); HD staff will have access to the algorithm in order to adjust UF rate accordingly. Following a one-month baseline observation period with usual care, subjects will undergo 4 weeks of each UF intervention administered in alternating weeks as described above, for a total study duration of 12 weeks. Data will be aggregated and results compared using a full month of data for each intervention.

**End of Study Procedures**—In order to maximize recruitment efficiency and the significant investment in undergoing ILR implantation, patients completing one study will be given the option of continuing to eligibility screening and enrollment for the alternate study. If subjects consent to both Study A and Study B, then the baseline observation period for the second study may be less than 1 month. Those refusing or ineligible will be offered ILR explanation.

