**Study Visit #4: Week 4 Reveal Visit (+/- 3 days)**

This visit will serve to review any adverse events, concomitant medications, and record dialysis treatment data from the baseline month of usual HD care. Subjects will be randomized to a treatment arm of Study A/B and will start study treatment on the next start of their short-interdialytic period (either Monday or Tuesday.) The Baseline Observation Period ends at this visit. Subjects should have completed at least 6 of their 12 scheduled dialysis treatments by this visit.

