**Study Visit #9: End of Treatment Visit**

Upon completion of either Study A or Study B, subjects will be screened and offered the opportunity to consent to participate in the other study. Subjects will be queried for adverse events and dialysis treatment records will be reviewed. If subjects elect to participate in both studies consecutively, then they will not need to redo the Week 1 Reveal insertion follow-up visits, since they will have already received a device. For subjects enrolling in both studies, a 1-week washout period is required (receive SOC hemodialysis treatment) and will then begin another 1-month of baseline monitoring prior to starting the intervention for the second study.

Once a subject has completed Study A and Study B, or a subject is no longer interested or eligible to participate in the second study, he or she will be given the option to come back to New York University Langone Medical Center for device removal. Subjects who choose to keep the device implanted after the last treatment will be followed for adverse events and concomitant medications for one week after this visit. Subjects who choose to have the device removed, will have two more study visits, one to remove the device and another to follow up on the removal procedure.

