**Safety** will be assessed by calculating the incidence rate (complications per unit follow-up time) for serious adverse events and intervention-specific complications. Comparisons of incidence rate between interventions will utilize Poisson regression adjusted for randomization scheme and site. Exploratory analyses will assess age, sex, race, mean intra-dialytic weight gain, potassium concentration and HCO3 concentration in month prior to randomization on the incidence of adverse events. Given the pilot nature of the trials and major goal of informing feasibility estimates for definitive trials, P<0.05 will be considered significant in all safety analyses. No adjustments will be made for multiple comparisons given the pilot nature of the studies.

**Efficacy** estimates for Aim 3 will utilize the mean duration of CSA as the primary outcome. In the event of incomplete follow-up, this will be indexed to duration of follow-up time (e.g. minutes per day). Change in CSA duration between interventions will be analyzed using mixed effects linear regression with terms for treatment, research site, period, sequence, and random effects for subjects. Primary outcomes for the dialysate trial will compare CSA during potassium maximization vs. minimization, and acidosis vs. alkalosis avoidance. For the UF trial, aggressive vs. conservative UF will be compared. Physiologically, the washout period of 1-week in the dialysate trial and 1 weekend in the UF trial is sufficient to avoid the possibility of carryover effects. Potential for sequence effects is minimized by a design with uniform sequences (all treatments appear once within each sequence). Potential for carryover and randomization sequence effects will be analyzed by including terms for sequence and their interaction with treatment in the models.

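### The secondary comparison of usual care with each intervention cannot use the primary mixed model: the baseline month is aliased with period, leaving only a non-randomised before-after contrast

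*Combined protocol and SAP*

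**What the plan says.** Under Secondary Analysis in Section VI: "Secondary analyses will compare CSA during usual care period and the individual interventions using identical methods". The only method this can refer to is the efficacy model earlier in Section VI, a "mixed effects linear regression with terms for treatment, research site, period, sequence, and random effects for subjects".

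In Study A (Section V), "After a month of usual care, subjects will cross-over in random order to four month-long periods". In Study B (Section V), "Following a one-month baseline observation period with usual care, subjects will undergo 4 weeks of each UF intervention administered in alternating weeks". Subjects are randomised at Study Visit #4, and of that same visit the plan says "The Baseline Observation Period ends at this visit". The usual-care month is therefore complete before any sequence is assigned.

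Balance is claimed for the randomised treatments only: "Potential for sequence effects is minimized by a design with uniform sequences (all treatments appear once within each sequence"). Usual care is not one of those treatments.

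Two other stretches of usual care exist. In Study A, "There will be a one-week washout with usual care between each intervention period"; these are weeks 9, 14 and 19. A subject who goes on to the other study has a one-week washout and "will then begin another 1-month of baseline monitoring prior to starting the intervention for the second study", although the End of Study Procedures paragraph in Section V allows that second baseline to be shorter than a month. The Secondary Analysis section speaks of a single usual-care period and names neither of these as data for the comparison. The plan does not say how period is coded.

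**The concern.** In a crossover, the period term separates treatment from time because each treatment appears in each period across sequences. That does not hold for the baseline month. Everyone receives usual care in it and no one receives an intervention, so a model with a separate level for each period cannot tell usual care apart from being in the first month after implant.

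An analyst who follows the text literally meets a rank-deficient model and must choose a way out that the plan does not give. Each way out gives a different answer, as shown below. The result could then be reported beside the randomised contrasts, in a pilot whose stated purpose is to supply effect-size data, with nothing to mark it as a before-after difference mixed with time since implant and study entry.

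**Working it through.** The plan gives no figure for this comparison, so there is nothing to reproduce first. The check is whether each contrast is identified by the model as written.

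**Inputs.** Two sites (Study Summary). Study A: baseline month plus four randomised months. Study B: baseline month plus two interventions, compared on a month of data each (Section V). 20 subjects per trial; the rank result does not depend on this number. Assumptions: period is categorical, and Study A uses a four-sequence balanced square (using all 24 orders gives the same conclusion).

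**Model.** For subject i in period j: y = mu + site + sequence + period(j) + treatment(i,j) + subject(i) + error. The baseline is j = 0, with treatment = usual care (UC).

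**Why it fails.** Add any constant c to period(0) and subtract c from treatment(UC). Every baseline row is unchanged, because it contains both terms. Every other row is unchanged, because it contains neither. The data therefore cannot fix treatment(k) − treatment(UC). A difference between two interventions does not involve c and stays identified.

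**Column counts** (intercept + site + sequence + period + treatment) and ranks:

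| Model | Columns | Rank | Contrast with UC |
|---|---|---|---|
| A, categorical period | 1+1+3+4+4 = 13 | 12 | not estimable (all four) |
| A, washout weeks added as UC, own period levels | 1+1+3+7+4 = 16 | 15 | not estimable |
| A, linear period, no washouts | 1+1+3+1+4 = 10 | 10 | estimable |
| A, linear time with washouts | 1+1+3+1+4 = 10 | 10 | estimable |
| B, monthly, categorical period | 1+1+1+2+2 = 7 | 6 | not estimable (both) |
| B, weekly, categorical period | 1+1+1+8+2 = 13 | 12 | not estimable (both) |
| B, monthly, linear period | 1+1+1+1+2 = 6 | 6 | estimable |

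In every categorical model, K-removal maximisation versus gradient minimisation, acidosis versus alkalosis avoidance, and restricted versus unrestricted UF remain estimable.

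The washout weeks do not help under categorical coding, because their period levels also contain nothing but usual care. Under linear coding the trend alone supplies identification: the Study A rank is 10 of 10 with or without the washouts.

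**What the ways out return.** Suppose no intervention has any effect and CSA drifts by 0, −20, −30, −40, −50 minutes over baseline and periods 1 to 4 of Study A. This drift is an illustration, not a figure from the plan.

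- Drop the whole period term: each intervention appears equally often in periods 1 to 4, so each shows (−20 −30 −40 −50)/4 − 0 = −35 minutes.
- Delete one period column to restore rank: that period is forced equal to baseline, and every intervention shows −20, −30, −40 or −50 minutes, depending on which column goes.
- Delete one treatment column instead: the contrasts are 0.
- Linear period: periods 1 to 4 lie on a line of slope −10, which extrapolates to −20 + 10 = −10 at baseline. Observed usual care is 0, so every intervention shows −10 minutes.

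The true effect is 0 throughout. The answer is set by the constraint chosen, not by the data.

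**The case against.** The best case against this point has five parts.

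1. *Usual care is not confined to the first month.* Correct for Study A, which has three washout weeks of usual care, and for subjects who enter both studies. A reader might infer that usual care occurs only at baseline; the documents do not support that. What stands is narrower: the single usual-care period named in the Secondary Analysis section appears to be the baseline month, and washouts given their own period levels do not remove the aliasing. A joint model of subjects who enter both studies, in both orders, could identify the contrast, but none is planned.

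2. *Period need not be categorical.* Also correct. A reader might infer that the comparison can never be estimated; that goes too far. With linear period it is estimable in both trials, but only through a trend assumption that the plan does not state.

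3. *Study B already has a randomised standard-of-care comparison.* Yes. The unrestricted UF arm carries the standard-of-care label, and restricted versus unrestricted is randomised and estimable. Only contrasts with the pre-randomisation month are affected.

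4. *The effect sizes for the definitive trials are safe.* Largely so. Aim 3 takes them from the randomised pairs, and nothing in the plan says that the usual-care contrast feeds a sample-size calculation. Section VI also labels all analyses exploratory. That label governs interpretation, however, and does not identify a parameter that the model cannot identify.

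5. *A statistician would notice.* Perhaps. A reader might infer that software will silently drop a column, but the plan names no package and some report the contrast as non-estimable. The instruction to use identical methods would still have to be abandoned after the data are in.

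**Conclusion.** The point stands as a defect of modest severity in one secondary analysis. With period as a class effect, all four Study A contrasts and both Study B contrasts against the baseline month are not estimable (rank one short of the column count in each trial). Without period, or with linear period, a number is obtained, but it is respectively a non-randomised before-after difference or one that depends on an assumed straight-line trend. The plan acknowledges neither.

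This rests on two readings: that the usual-care period means the baseline month, and that period is categorical. Both are the natural readings, and neither is stated. The primary randomised comparisons are unaffected.

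**What to change.** In the Secondary Analysis section, stop applying the instruction to use identical methods to this comparison, and treat both trials alike:

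- Report baseline month versus each intervention as a descriptive, non-randomised before-after change in CSA minutes per monitored day, with an estimate and interval, and with no P value or treatment-effect claim.
- State that this change is not to be used as an effect size for the definitive trial.
- State how period is coded in the primary model.
- Optionally, in Study A, prespecify a sensitivity model with a linear time trend that adds the washout weeks as usual care, weighted by monitored days. State that the linear trend identifies the contrast and that the washout data only reduce reliance on extrapolation.

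This costs SAP wording only and needs no new procedure, since loop-recorder monitoring continues through the washouts. The downsides are a weaker claim for this secondary comparison and, in the optional model, the linearity assumption and short washout weeks that may carry residual effect from the preceding period. Weighting matters there because one-week and one-month observations would be mixed for a very skewed outcome (Section VI cites 356 ± 1765 minutes).

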## **VII. RISKS AND DISCOMFORTS**

### Risk to Human Subjects

The overall risks of the interventions proposed in this application are minimal. Informed consent will be obtained from all subjects, and regular monitoring will occur in order to prevent or minimize study-associated risks.

While ILR insertion is a pre-requisite that may add minimal risk and POC testing is a research-based measure, all of the randomized interventions to be studied—i.e. the protocol-driven manipulation of the

dialysis prescription—are consistent with standard care of care dialysis practices. Thus, the proposed trials are best considered to be comparisons of standard therapies rather than studies of experimental or novel therapies that might have added risk due to their unstudied or experimental nature.

Inclusions and exclusion criteria have been limited in order to maximize generalizability, and have been designed to ensure that enrolled subjects are suitable for the intervention (e.g. that mean intra-dialytic weight gain is sufficient to justify an UF rate  $\geq 13$  mL/hour/kg), to maximize safety (e.g. exclusion of subjects with recent severe hyperkalemia), to ensure that subjects can provide informed consent (e.g. exclusion of potentially vulnerable populations such as prisoners, or mentally incapacitated subjects), and to ensure that subjects are expected to continue dialysis and survive long enough to complete the trials (exclusion of patients with expected survival  $< 6$  months, exclusion of patients with impending transplant). Enrollment will be 5 months in the dialysate interventions trial and 3 months in the UF trial. Data shared between sites from these trials will be de-identified with the code stored locally.

**Potential Risks**—Potential risks to participants include: (i) risks from phlebotomy; (ii) potential side effects from ILR insertion; (iii) risks from algorithm-based management of dialysate potassium and bicarbonate prescriptions; (iv) risks from algorithm based management of UF rate and (iv) the chance that personal information is lost or confidentiality is breached. Each of these risks is discussed below.

**i. Phlebotomy:** Momentary discomfort as well as bruising may occur during routine phlebotomy. To eliminate this risk, we will obtain blood through the patients' vascular access while they are receiving dialysis, and there will be no access of the dialysis access or venipuncture purely for study purposes. We plan to use the minimal amount of blood necessary for POC testing, which is  $<1$  mL (100  $\mu$ L). The total amount of blood required for testing over 5 months will be approximately 52 mL. This is unlikely to cause a significant change in blood counts or symptomatic anemia, and the risks associated with this degree of blood loss can be considered minimal. Risk will be further minimized by putting the protocol on hold for subjects with severe anemia (defined as hemoglobin  $<8$  mg/dL) on the most recent (monthly) standard of care labs and resuming only when anemia resolves.

**ii. ILR insertion:** ILR insertion requires administration of local anesthesia or conscious sedation and a small subcutaneous puncture for device placement. Risks of local anesthesia are minimal but could include very rare allergic reactions to subcutaneous anesthetic agents (subjects will be screened for anesthetic allergy). Transient bruising and discomfort is expected and will be treated as needed with over the counter agents. Prior investigator experience with ILR devices suggest that more significant complications such as discomfort requiring explanation and bacteremia are very rare. Local infection may occur. Prior experience suggests that even in the dialysis population these are typically mild infections which are treatable with oral antibiotics and do not require device removal. These risks will be disclosed to subjects. Subjects with conditions that place them at high risk of infection (e.g. severe psoriasis, multiple prior infections, immunosuppression) will be excluded to further minimize risks. Finally, subjects will be assessed within 1 week after device implantation and at 1 month to assess for proper wound healing and to allow early identification and treatment of infections.

**iii. Side effects of potassium, bicarbonate, and UF interventions:** As reviewed in the above plan, each of the algorithms is designed to lower the risk of arrhythmia. Although each is being used within the context of a research study, each algorithm prescribes treatments fully consistent with standard of care dialysis. In theory, the risk of arrhythmia may be increased by mandating a protocol-driven specific choice of therapy from among the available standard of care options. It is uncertain whether this is materially different in nature or degree from the risk patients are routinely exposed to outside of a research environment when physicians in clinical practice currently assign the dialysis prescription at the beginning of each month rather than at each individual session. Therefore, research-associated risks are low and within generally acceptable ranges for research—particularly given the importance of the knowledge to be gained. Potential risks will be further minimized by having the DSMB review all deaths and arrhythmia-related hospitalizations during the study. Events will be reviewed within 1 week in order to assess for potential relatedness, and the DSMB will provide recommendations on the need to halt the study or revise the protocol, or need for ad-hoc review by the DSMB of un-blinded data.

**Study A potassium and bicarbonate algorithms** may result in significant abnormalities in serum bicarbonate or serum potassium level. Once again this risk, though real, is not materially different than the risk of developing significant electrolyte abnormalities in routine practice in which bicarbonate and potassium may be measured only once a month with dialysis prescription based on that single value.

Study procedures ensure testing of electrolytes at each session (3x/week) in contrast to a frequency of as little as 1x/month in routine practice. Severe electrolyte abnormalities will thus be recognized earlier with study patients than in routine practice. Similarly, POC testing will ensure that the dialysis prescription will be adjusted according to the ambient potassium or bicarbonate at that dialysis session. In routine practice, follow-up testing at outpatient dialysis units typically has a turn-around time of hours (stat testing) or days (routine lab draws) which makes appropriate adjustment of the dialysis prescription unfeasible. Thus, study procedures may actually lower the risk of severe electrolyte abnormalities or risk of complications from those abnormalities. However, significant inaccuracy in the point of care testing results could modify the associated risks.

To further mitigate risk, patients with severe abnormalities in potassium ( $K>6.5$  or  $<3.0$ ) or bicarbonate ( $<20$  or  $>32$ ) will temporarily come off therapy and be treated off-protocol at the discretion of their clinician.

**Study B UF algorithms** are designed to either limit UF rates to  $\leq 10$  mL/kg/hour or to allow UF rates  $\geq 13$  mL/kg/hour. As discussed in the research summary, there is significant equipoise regarding the risk/benefit ratio of either strategy, as the use of high UF rates minimizes the risk of volume overload at the expense of rapid fluid shifts, whereas limiting UF rate minimizes the risk of rapid fluid shifts at the expense of increasing the risk of volume overload. Both strategies are routinely employed in clinical care. Thus, it is again unclear whether research-related risks are materially different than those in routine practice. As described in the Research Plan, subjects will cross over weekly between the unlimited and restricted UF treatments, thereby allowing removal of excess fluid accumulated during the restrictive week during the subsequent, unlimited week. This will limit any excessive fluid gains to a maximum of a few liters over the course of the restricted UF week thereby limiting the possibility of volume-related complications in the event patients fail to self-regulate intake of salt and water. Safety, will be further ensured because patients who show signs of significant volume overload will have the

potential to schedule an extra UF session as needed (outside of the protocol) in the event that symptoms of volume overload are intolerable. Lastly, all hospitalizations for myocardial infarction or heart failure will be reviewed by the DSMB. Events will be reviewed within 1 week in order to assess for potential relatedness, need to halt the study or revise the protocol, or need for ad-hoc review by the DSMB of un-blinded data in order to protect research subjects.

**iv. Breach of confidentiality:** Inadvertent release of information about medical history, laboratory information, or test results poses a psychological/financial risk. To maintain confidentiality and minimize risks to privacy, data will be de-identified and stored using a unique, coded study identifier for each subject. All data will be stored on password-protected servers and will be protected behind medical center fire walls and with contemporary virus software. Only the study staff will have access to the network drive. The only individually identifiable data that will be collected are names, medical record numbers, addresses, and contact phone numbers. These data are required for patient follow-up and for use during registration in the hospital information systems prior to ILR insertion. The file linking the study ID and personally identifiable information will be kept by the PIs in a similarly secure network drive location with access limited to the PIs and study coordinators or staff with responsibility for contacting patients. This file will be accessed only as necessary for patient follow-up or safety concerns. All other recorded data will be identified by study number only, and will be housed separately from data containing patient identifiers. Only the principal investigator (or personnel responsible for contacting patients) will have access to cross-reference the files. Sharing of data between Duke and NYU will involve only de-identified data. REDCAP or other electronic data capture instruments will be used to record study data and create a single, study database.

